#### Hydrocortisone Dose Adjustment During Conventional Treatment

We will attempt to optimize the child's management during a baseline period. While administering hydrocortisone (preferably in a dose of 10-15 mg/m^2/day, and not exceeding 25 mg/m^2/day), the mineralocorticoid dose will be adjusted to maintain a normal plasma renin activity in children with 21-hydroxylase deficiency. With plasma renin activity in the normal range, hydrocortisone dose will generally be increased if:

(1) the growth rate is 2 standard deviation (SD) units or more above the median normal value for age;

(2) the rate of bone age advancement exceeds 2 years per chronologic year; or

(3) plasma 17-hydroxyprogesterone (17-OHP) levels are excessively elevated in association with growth rate and rate of bone maturation that are above the median normal values.

Because spot measurements of plasma 17-OHP correlate rather poorly with growth rate and bone maturation, plasma 17-OHP will be used as an aid to judgement rather than as a treatment goal in itself. At the present time, 0800-0900 plasma 17-OHP levels of 500 to 1300 ng/dL are considered appropriate, levels of 1300 to 3000 ng/dL prompt consideration of a hydrocortisone dose increase (assuming that plasma renin activity is normal), levels of 3000 to 6000 ng/dL prompt strong consideration, and levels >6000 ng/dL will ordinarily lead to a dosage increase.

Hydrocortisone dose will generally be decreased if:

(1) the growth rate is 2 SD units or more below the median normal value for age, if the bone age is prepubertal, or the growth rate seems inappropriately suppressed relative to age and bone age, if the bone age is in the pubertal age range;

(2) the body mass index exceeds 2 SD units above the median value for age, or if signs of Cushing's syndrome are appearing;

(3) there is no detectable bone maturation over a period of more than 6 months; or

(4) plasma 17-OHP appears excessively suppressed in association with a subnormal growth rate or rate of bone maturation. Plasma 17-OHP levels below 500 ng/dL will ordinarily raise consideration of a dosage decrease; levels below

200 ng/dL will raise strong consideration.

We have chosen a thrice-daily hydrocortisone dose schedule for this study. There are no controlled studies that compare a twice-daily and thrice-daily approach; however the thrice-daily hydrocortisone dose schedule is the most commonly used conventional regimen.

#### Hydrocortisone Dose Adjustment During Investigational Treatment

Congenital adrenal hyperplasia occurs in several clinically distinct variants that reflect differing severity of the underlying enzymatic deficiency, even among the classic forms. For example, the salt-wasting and simple-virilizing forms of 21-hydroxylase deficiency have different clinical courses: salt-wasters experience many more episodes of adrenal crisis and may require more glucocorticoid for adequate control. Even within the salt-waster and simple-virilizer subgroups of CAH, clinical heterogeneity is seen. This may be due to varying genotypes or other unknown factors.

A hydrocortisone dose of 8 mg/m2/day was chosen in our initial pilot study based on estimates of normal production rate; however, children may vary in their glucocorticoid daily requirements. Our hypothesis that the regimen of flutamide, an aromatase inhibitor and a reduced hydrocortisone dose can normalize the growth of children with, CAH while avoiding the complications of supraphysiologic glucocorticoid, does not require identical glucocorticoid doses in all children on the new regimen. Regimens will be more closely tailored to the individual differences in glucocorticoid requirement. The hydrocortisone dose will be allowed to vary in the flutamide-aromatase inhibitor treatment arm.

With plasma renin activity in the normal range, hydrocortisone dose will generally be increased if 2 or more of the following occur:

- 1) the rate of bone age advancement exceeds 2 years per chronologic year and there is no evidence of central precocious puberty as the cause;
- 2) plasma 17-hydroxyprogesterone levels exceed 10,000 ng/dL;
- 3) plasma androstenedione levels exceed 400 ng/dL;
- 4) testosterone levels exceed 100 ng/dL in girls or prepubertal boys;

- 5) signs of virilization (clitoral growth, voice deepening, acne) on physical examination;
- 6) presence of adrenal rest tissue on testicular ultrasound in boys (see below);
- 7) evidence of macronodular disease on adrenal ultrasound or MRI (see below).

With plasma renin activity in the normal range, hydrocortisone dose may be decreased if 2 or more of the following occur:

- 1) plasma 17-hydroxyprogesterone levels are below 500 ng/dL;
- 2) plasma androstenedione levels are below 50 ng/dL;
- 3) the rate of bone age advancement is less than 1 year per chronologic year;
- 4) weight percentile is greater than or equal to height percentile.

### Treatment of Testicular Adrenal Rest Tissue or Macronodular Disease.

Testicular ultrasound is a sensitive method for detecting testicular adrenal rest tissue; however, testicular ultrasounds are not routinely done on CAH patients and the incidence of adrenal rest tissue with this sensitive method is unknown. Typically, testicular adrenal rests are thought to be evidence of poor control, but this may only be the case if significant growth occurs. If a small amount of adrenal rest tissue is present, and there is no growth over time, a change in treatment may not be necessary. Our studies of male patients with CAH support this approach [41]. If interval growth occurs between visits (i.e. over 6 months), glucocorticoid dose will be increased 20%, or to a minimum of 12 mg/m2/day in the flutamide-aromatase inhibitor group. If interval growth occurs on a hydrocortisone dose of at least 12 mg/m2/day in the flutamide-aromatase inhibitor treatment group, or 18 mg/m2/day in the conventional treatment group, then a 10-day course of dexamethasone (15 mcg/kg/day given qhs) will be instituted. Flutamide and aromatase inhibitor therapy will be continued.

If the rare occurrence of adrenal macronodular disease develops, a 10 day course of dexamethasone (15 mcg/kg/day given qhs) will be instituted. Subsequently, glucocorticoid dose will be increased to a minimum of 12 mg/m2/day in the flutamide-aromatase inhibitor treatment group, and flutamide and aromatase inhibitor therapy will be continued. Glucocorticoid dose will be increased to a minimum of 15 mg/m2/day in the conventional treatment arm.

The boy with significant testicular adrenal rest tissue and the patient who is developing macronodular enlargement represent special cases in which it may not be appropriate to restrict hydrocortisone dosage to the physiologic range. Fortunately, this is a small proportion of patients with CAH. We recognize that the final analysis of the data will need to take account of these subgroups.

#### Monitoring and Criteria for Withdrawal of Subjects from Study

Patients will be monitored every 3 months, with visits alternating between their local physician and NIH (every 6 month visit to NIH). At the visit to the local physician, a single blood sample

will be obtained and sent to NIH for analysis of the same hormonal measures and blood chemistries that are performed during NIH visits (see protocol section above). The other monitoring during NIH visits has been described in detail above.

In addition to this monitoring, patients who are randomized to flutamide will receive intensive monitoring of liver function as a precaution against flutamide-associated liver toxicity (see Risks below). This monitoring will consist of a blood sample to determine liver function every 2 weeks for the initial 3 months, every month for the next 9 months, and every 3 months thereafter.

Patients who experience flutamide-associated liver toxicity (the estimated incidence is 1 in 273 patients), or who do not tolerate the flutamide and aromatase inhibitor regimen, will be withdrawn from this treatment arm and followed on conventional treatment so that their outcome will be available for an intention-to-treat analysis. We will also ask patients who elect to withdraw from the study to continue to make semiannual height measurements at home and to return to NIH for one final height and weight measurement once they attain the final height criteria.

Since CAH is a chronic disorder requiring lifelong treatment, and since the final height of all subjects is important for the performance of an intention-to-treat analysis, we do not foresee circumstances that would lead us to withdraw a subject from study. If an unrelated illness, such as chronic active hepatitis, were to preclude use of the investigational regimen, we would nonetheless wish to follow the subject on the conventional treatment.

### Adverse Event Reporting and Data Monitoring

Reportable events will be tracked and submitted to the IRB as outlined in Policy 801. the primary investigator is responsible for monitoring the protocol.

is responsible for all aspects of the study.

are responsible for coordinating data collection and will review the data for accuracy and completeness within 1 month of each subject visit, including review of patient consent documents. Review of literature and results of related studies will be assessed throughout the study for any impact on patient safety or ethical questions.

is responsible for maintaining IRB documentation, including records of all reviews of the study and submissions to the IRB.

Missed blood draws or other testing (i.e. radiological studies) due to scheduling or patient related issues commonly encountered in clinical care will not be reported as protocol deviations.

will maintain subjects' records for at least three years after completion of the study.

## Waiver of consent for minors when they reach the age of majority

When a pediatric subject reaches age 18, continued participation (including ongoing interactions Page 17 of 26 with the subject or continued analysis of identifiable data) will require that consent be obtained from the now adult with the standard protocol consent document to ensure legally effective informed consent has been obtained.

If reconsent is not feasible, we request waiver of informed consent to continue to use data and/or specimens for those individuals who become lost to follow up or who have been taken off study prior to reaching the age of majority.

Requirements for Waiver of Consent consistent with 45 CFR 46.116 (d):

- (1) The research involves no more than minimal risk to the subjects.
  - a. Analysis of samples and data from this study involves no additional risks to subjects.
- (2) The research could not practicably be carried out without the waiver or alteration.
  - a. Considering the length of time between the minor's last contact with the research team and their age of majority, it will likely be very difficult to locate them again. A significant reduction in the number of samples analyzed is likely to impact the quality of the research.
- (3) As the research involves using identifiable private information or identifiable biospecimens, the research could not practicably be carried out without using such information or biospecimens in an identifiable format.
  - a. Though the purpose of future studies cannot yet be known, they often involve the correlation of clinical outcomes and clinical interventions with laboratory studies. Such information would be unavailable if access to medical record numbers was unavailable.
- (4) The waiver or alteration will not adversely affect the rights and welfare of the subjects.
  - a. Retention of these samples or data does not affect the welfare of subjects.
- (5) Whenever appropriate, the subjects will be provided with additional pertinent information after participation.
  - a. We only request a waiver of consent for those subjects who have been lost to follow-up or who have been taken off study prior to reaching the age of majority.

## Research Use, Storage and Disposition of Human Subjects' Samples and Data

Samples will be stored according to NICHD and NIH policy. Samples may be used in the future, with identifiers, for studies not described here, based on the subject's consent. Blood samples may be shared with collaborators, without personal identifiers.

All of the stored study research specimens are labeled by a numeric, alpha-numeric identification code that only the study team can link to the subject. Specimens are stored in locked lab freezers and in the NICHD biorepository, which is accessed via a locked door. All stored research specimens are logged into a specimen tracking database. Variables included in the database are ID, specimen type, aliquot, date of collection, and location. All usage and/or disbursement of the specimens is documented and tracked in the database. Only investigators or their designees will have access to the specimens and/or data.

Subject confidentiality will be maintained to the greatest extent possible. Research results will be Page 18 of 26

labeled using a unique code. Publications will not include subject names nor will they contain personal identifying information.

Any loss or unanticipated destruction of specimens (e.g. due to freezer malfunction) or data (e.g. misplacing a print-out of data with identifiers) that would affect the scientific integrity of the study will be reported to the IRB as an unanticipated problem by the PI.

This protocol will be kept open as long as there is a possibility of future research use of the specimens and/or data. When there is no longer a need, the specimens will be destroyed or, after IRB approval, transferred to another repository. Data will be archived by the investigator in compliance with requirements for retention of research records, or after IRB approval, destroyed or transferred to another repository.

#### Analysis of Study (please also see attached SAP Appendix A)

- The primary outcome (adult height expressed in SD units) will be compared between groups at the conclusion of the study using the unpaired two-tailed Student's t-test, or nonparametric Wilcoxon rank sum test, as appropriate
- Secondary outcome measures during the study include hormone levels (percent of visits in ranged defined above) and treatment doses, BMI (as SD units), final BMD (Z-score), growth velocity (in SD units), rate of bone maturation, and predicted adult height (Bayley-Pinneau method, automated software in a subset of patients) at baseline, pubertal onset, and final visit. These outcomes will be compared between the study arms by multivariable mixed models for repeated measures. These models will allow for within-subject comparisons between timepoints, as well as account for their correlations across time, adjust for potential confounders, and specify the appropriate outcome distribution (e.g., normal, binomial, or Poisson distribution for type of data). They are a robust method for accommodating missing data, especially in measures that are repeated and collected longitudinally. Post-hoc comparisons will identify the driving factors and group effect influencing any observed differences, and will be corrected for multiple comparisons as applicable.

We have chosen a group size of 30, giving this study the same statistical power as the study of Deslorelin-induced pubertal delay (83-CH-199). With an expected standard deviation of 6 cm for the final height measurements (approximately that of the normal population), the group size required to give a 80% power to detect a 5-cm difference (about 2 inches) at a p<0.05 is 24. The group size needed to detect a 6-cm difference is 17. This is regarded by the pediatric endocrine community as a reasonable power for a growth study - for example, the Genentech Collaborative Study of Turner Syndrome had a group size of 17. Thus, the study is designed to detect at least a 5 cm difference in final height, a clinically meaningful difference, and allows for a 25% drop out rate over the course of the study. This is regarded by the pediatric endocrine community as a reasonable power for example, the Genentech Collaborative Study of Turner Syndrome had a group size of 17. Thus, the study is designed to detect at least a 5 cm difference in final height, a clinically meaningful difference, and allows for a 25% drop out rate over the course of the study - for example, the Genentech Collaborative Study of Turner Syndrome had a group size of 17. Thus, the study is designed to detect at least a 5 cm difference in final height, a clinically end by the pediatric endocrine community as a reasonable power for a growth study - for example, the Genentech Collaborative Study of Turner Syndrome had a group size of 17. Thus, the study is designed to detect at least a 5 cm difference in final height, a clinically meaningful difference, and allows for a 25% drop out rate over the Degree **19** of **26** 

Abbreviated Title: Congenital Adrenal Hyperplasia Version Date: 03/23/2023

course of the study.

Please find attached study analysis plan.

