#### Principal Investigator:

[name]

**Number and type of patients**: 62 patients with Congenital Adrenal Hyperplasia Accrual Ceiling: 62

	Number	Sex	Age Range
Patients	62	male and female	ages 2-18
Volunteers	0	V U	-

Multi-site study: No

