# **B** Secondary Endpoints

Secondary outcome variables will be examined between the two study arms at baseline, pubertal onset and adult height (final visit). To examine sex differences, the secondary outcomes variables will be examined by-sex between the two study arms.

'Pubertal Onset' is defined as the visit when patients entered puberty (Tanner 2 breast in females, testicle size > 3mL) or completed therapy with the aromatase inhibitor and or LHRHa.

- i. Adult height achieved will also be expressed standard deviation (SD) units and in cm as the difference in height achieved in relation to their target height (i.e., mid-parental height, calculated based on their parental heights)
- ii. Height achieved (SD units) from baseline to pubertal onset
- iii. Height achieved (SD units) from pubertal onset to adult height
- iv. Predicted adult height (using Bayley-Pinneau method) at pubertal onset
- v. Predicted adult height (using Bayley-Pinneau method) change from baseline to pubertal onset
- vi. Predicted adult height (using Bayley-Pinneau method) change from pubertal onset to final height
- vii. Growth velocity (in SD units) from baseline to pubertal onset
- viii. Growth velocity (in SD units) from pubertal onset to adult height
- ix. Percent of visits with ACTH in normal range from baseline to pubertal onset
- x. Percent of visits with ACTH in normal range from pubertal onset to adult height
- xi. Percent of visits with androstenedione in normal range from baseline to pubertal onset
- xii. Percent of visits with androstenedione in normal range from pubertal onset to adult height
- xiii. Percent of visits with 17-hydroxyprogesterone in the optimal range (<1,200 ng/dL) or high (>1,200 ng/dL) from baseline to pubertal onset
- xiv. Percent of visits with 17-hydroxyprogesterone in the in the optimal range (<1,200 ng/dL) or high (>1,200 ng/dL) from pubertal onset to adult height
- xv. Percent of patients with onset of central precocious puberty (CPP)

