During flutamide and aromatase inhibitor treatment hydrocortisone dose will be decreased in 4 equal weekly steps to approximately 8 mg/m^2/day. During this month close contact will be maintained with the family by telephone and/or outpatient visits (for local patients), or referring physician visits (for distant patients), to check for symptoms or signs of adrenal insufficiency. If the hydrocortisone dosage of approximately 8 m^2/day produces symptoms or signs of adrenal insufficiency in any subject, the dosage will be adjusted on an individual basis to a dosage that will not cause symptoms or signs of adrenal insufficiency.

Patients will initially be placed on Testolactone 20 mg/kg/day of testolactone. The dose will then be increased at weekly intervals to 30 and then 40 mg/kg/day, which will be the maximum dose for the study (approximately equivalent to the usual maximal adult dose of 2 grams per day).

Patients placed on letrozole will receive a dose comparable to the dose used to suppress estrogens in adult women (1.5 mg per square meter of body surface area). This is the same dose of letrozole used for the treatment of girls with McCune Albright Syndrome.

Flutamide will also be administered in increasing doses. Patients will initially be placed on 5 mg/kg/day of flutamide. The dose will then be increased at weekly intervals to 7.5 and then 10 mg/kg/day, which will be the maximum dose for the study. This is approximately the same dose used to treat men with prostate cancer (750 mg/day, or about 10 mg/kg/day).

Subjects will be evaluated as outpatients, day-hospital patients, or inpatients on the pediatric endocrine ward at 6-month intervals until final adult height is attained. The following evaluations will be made:

- (1) Ten standing height measurements by stadiometer.
- (2) Ten sitting height measurements.
- (3) Weight.
- (4) Bone age.
- (5) Two 24-hour urine collections for cortisol.

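### The primary comparison of adult height is unadjusted: valid, but a prespecified ANCOVA on three baseline predictors would be more precise if they explain more than about 5–8% of the variance

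*Combined protocol and SAP*

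**What the plan says.** Analysis of Study states that adult height in SD units "will be compared between groups at the conclusion of the study using the unpaired two-tailed" t-test, or by a Wilcoxon test where suitable. It names no covariate for this comparison. The next item in that section gives the secondary outcomes mixed models that "adjust for potential confounders".

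Predictors of adult height are largely in hand. The evaluation list under Protocol includes "Ten standing height measurements by stadiometer" and bone age. Secondary endpoint i expresses adult height as the "difference in height achieved in relation to their target height (i.e., mid-parental height, calculated based on their parental heights". Parental heights are therefore needed, although they do not appear in the evaluation list.

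On size, the title page reads "62 patients with Congenital Adrenal Hyperplasia Accrual Ceiling: 62". The sample-size text chooses 30 per arm, requires 24 per arm for 80% power to detect 5 cm with an SD of 6 cm, and says the design "allows for a 25% drop out rate over the course of the study". The section on withdrawal plans follow-up of children who leave the regimen and asks those who withdraw "to return to NIH for one final height and weight measurement once they attain the final height criteria".

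The section refers to an attached SAP, Appendix A, which was not in the text reviewed.

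**The concern.** The outcome on which the trial is judged is the one with no stated adjustment. The documents themselves treat parental height and bone maturation as informative: the Introduction cites adult height corrected for parental height and says that accelerated bone maturation compromises adult height. Patient Selection admits bone ages from 2 to 13 in boys and 2 to 11 in girls, so children enter at very different stages of growth.

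This is not a question of bias. Under randomisation the t-test's standard error already allows for chance imbalance. What may be lost is precision, in a trial that cannot buy it with more children.

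Secondary endpoint i uses target height, but only as a difference. That fixes the slope on target height at 1 instead of estimating it, and it leaves the primary test unchanged.

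**Working it through.** **Inputs from the sample-size text.** Difference 5 cm, SD 6 cm (d = 5/6), two-sided alpha 0.05, 30 per arm planned, 25% dropout. **Assumed, because the documents give none:** R², the share of within-arm variance explained by the covariates, at 0, 0.1, 0.2 and 0.3.

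**1. The plan's own figures.** With the noncentral t, 80% power needs 24 per arm for 5 cm and 17 per arm for 6 cm. Both match the plan. Unadjusted power for 5 cm at 24 per arm is 80.7%.

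**2. Formulae**, with n per arm and N = 2n:
- Unadjusted: noncentrality d·√(n/2), df = N − 2.
- ANCOVA with k covariates: variance multiplied by V = (1 − R²)(N − 3)/(N − 3 − k), noncentrality d·√(n/2)/√V, df = N − 2 − k. The factor (N − 3)/(N − 3 − k) is the penalty for chance covariate imbalance.

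Example, n = 24, k = 3, R² = 0.2: the unadjusted noncentrality is 0.833 × √12 = 2.89; V = 0.8 × 45/42 = 0.857; the adjusted noncentrality is 2.89/√0.857 = 3.12 on 43 df. Power is 86.2%.

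**3. Power with three covariates**

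| Per arm | Unadjusted | R² = 0 | 0.1 | 0.2 | 0.3 |
|---|---|---|---|---|---|
| 22 | 77.0% | 73.7% | 78.1% | 82.7% | 87.3% |
| 24 | 80.7% | 77.8% | 82.0% | 86.2% | 90.3% |
| 30 | 88.8% | 87.0% | 90.2% | 93.2% | 95.8% |

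**4. Half-width of the 95% CI with three covariates, in cm**

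| Per arm | Unadjusted | R² = 0.1 | 0.2 | 0.3 |
|---|---|---|---|---|
| 22 | 3.65 | 3.61 | 3.40 | 3.18 |
| 24 | 3.49 | 3.43 | 3.23 | 3.03 |
| 30 | 3.10 | 3.03 | 2.85 | 2.67 |

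**5. Break-even R².** By variance alone it is k/(N − 3): 3/41 = 0.073, 3/45 = 0.067 and 3/57 = 0.053 at 22, 24 and 30 per arm. Allowing also for the lost degrees of freedom, it is 0.077, 0.069 and 0.054.

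**6. Equivalent sample size.** At R² = 0.2, ANCOVA with 30 per arm has the power of an unadjusted test with 35.3 per arm. That is 2 × 35.3 ≈ 71 children, above the ceiling of 62.

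**7. Dropout.** 30 × 0.75 = 22.5 per arm, below the 24 required. If every dropout lacked an adult height, unadjusted power would be 77.0–78.9% at 22–23 per arm. Starting from 31 per arm, 31 × 0.75 = 23.25 and power is 79.4%.

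**8. A fourth covariate.** At R² of 0.1/0.2/0.3 power is 76.9/81.6/86.4% (22 per arm), 81.0/85.3/89.6% (24) and 89.6/92.7/95.5% (30). Break-even R² rises to 0.102, 0.093 and 0.073. If the covariates predict nothing, the loss is 4.5, 3.9 and 2.4 points.

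**9. Simulation.** With 40,000 trials per cell and independent normal covariates, simulated powers agree with the formula to within about 0.6 points. In separate runs of 20,000 trials, type I error was 0.047–0.052 for the t-test and 0.048–0.053 for ANCOVA. Both are valid.

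**The case against.** The strongest reply is that there is no error here. The test is standard and valid, and the sample size was computed for that same unadjusted comparison. Both statements are true, so the point is an improvement and not a correction.

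Other points that stand:
- **Appendix A.** Covariates may be specified there. The absence of adjustment is established only for the protocol text.
- **R² is unknown.** A gain worth having needs about 0.2. The Introduction describes rapid early growth followed by short adult stature, so early height SD score may predict adult height poorly. Filling in missing parental heights would lower R² further, by an amount not computed here.
- **Power may already suffice.** With all 30 per arm observed it is 88.8%. The 77–79% case is a worst case, because the plan follows children who leave the regimen and seeks a final height from those who withdraw.
- **It may be late.** The version is dated March 2023, parts of the endpoint text are in the past tense, the trial is open-label, and a monitoring committee evaluates the data annually. The documents do not say whether adult heights have been compared by arm. Changing a primary analysis after such a look would cost credibility.
- **A fourth covariate weakens the case.** At 22 per arm and R² of 0.1, ANCOVA gives 76.9% against 77.0% for the t-test.

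These points limit the size of the benefit and set conditions on the change. They do not defeat the conditional claim: above the break-even R², the planned test gives up precision that data largely in hand could supply.

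**Conclusion.** The concern holds as a matter of precision. The plan should be changed if no between-arm look at adult height has taken place, but the trial is not invalid without the change.

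At the assumed R² of 0.2, three covariates add 5.7 points of power at 22 per arm (77.0% to 82.7%), 5.5 at 24 (80.7% to 86.2%) and 4.4 at 30 (88.8% to 93.2%). At R² of 0.3 the gains are 10.3, 9.6 and 7.0 points. At 0.1 they are about 1–1.5 points. If the covariates predict nothing, the losses are 3.3, 2.9 and 1.8 points. A narrower interval is useful even where power is already adequate.

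Confidence is medium. The conclusion rests on the plan's 5 cm and 6 cm, on an R² that the documents do not give, and on Appendix A not already adjusting the primary analysis.

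**What to change.** Make the primary analysis an ANCOVA of adult height SD score on randomised arm, and fix the following in advance:

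- **Covariates:** target-height SD score, height SD score, and bone age minus chronological age. The last does not capture stage of growth at entry. If that is wanted, add bone age or chronological age and accept one more degree of freedom; decide this now.
- **Baseline:** the randomisation visit, before study drug starts. The plan describes optimising the child's "management during a baseline period" before randomisation and does not tie baseline to a visit. This matters once baseline values enter the primary model.
- **Missing parental heights:** fill with the mean target-height SD score over both arms combined, without reference to arm. Add parental heights to the evaluation list.
- **Reporting:** give the adjusted difference with its 95% CI, and keep the t-test or Wilcoxon test as supportive.
- **Timing:** fix this before any between-arm look at adult height, and record which outcomes were already known. The trial is open-label and data are reviewed within a month of each visit. If adult heights have already been compared by arm, keep the planned test as primary and label the ANCOVA supportive.
- **Appendix A:** if it already adjusts the primary analysis, align the protocol text with it.

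The cost is a protocol and SAP amendment and a check that parental heights are on file. The statistical cost is 3 degrees of freedom and about 2–3 points of power if the covariates predict nothing, or 4 degrees of freedom and about 2–4.5 points with the fourth covariate.
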